9.3 Exploratory Analyses

9.3.1 To assess the feasibility of conducting a telehealth support group for cancer survivors within a pandemic, we will measure how many subjects are still participating at the final visit (Visit 8); the proportion of subjects who are active at this visit can be calculated as n/enrollment (with the expectation of approximately 15 enrolled). When the sample size is 15, a two-sided 95% confidence interval for a single proportion will extend 25.3% from the observed proportion for an expected proportion of 50%; if the proportion is low or high, such as 10% or 90%, a two-sided 95% confidence interval will extend 15.2% from the observed proportion. These data could be used in sample size calculations to design future studies.

9.3.2 To assess YA cancer survivors' interest in participation in a telehealth support group within a pandemic, the data would be used to estimate the percentage of sessions attended for each participant and calculate the mean participation rate and standard deviation; these data could also be expressed as mean number of visits and standard deviation. These data could be used to help design future studies.

9.3.3 To enhance participants' strategies for engaging social connectivity and reduce feelings of isolation amidst simultaneous forces promoting self-isolation (i.e., cancer diagnosis and pandemic), the UCLA Loneliness Scale will be used. As this is a continuous measure, with an n of 15, the width of the confidence interval around the baseline, Visit 4, Visit 8, and change between baseline and Visit 4 as well as Visit 8 scores would be approximately 1.02 standard deviations; a paired t-test will be used to assess the change in the scores. As this is a pilot study, no adjustment in the p-value will be done for multiple comparisons.

Cancer within a Pandemic: A Telemental Health Intervention Designed to Augment Psychological Resilience amidst Dual Health Threats

Wake Forest Baptist Comprehensive Cancer Center
WFBCCC #01520

9.3.4 To observe improvement in psychological resilience and flexibility skills in participants, the Acceptance and Action questionnaire (AAQ) will be used to estimate flexibility. As in 9.1, with an n of 15, the width of the confidence interval around the baseline, Visit 4, Visit 8, and change between baseline and Visit 4 and baseline and visit 8 scores would be approximately 1.02 standard deviations; a paired t-test will be used to assess the change in AAQ. As this is a pilot study, no adjustment in the p-value will be done for multiple comparisons.

9.3.5 To reduce feelings of helplessness and hopelessness, the MINI MAC will be used. With an n of 15, the width of the confidence interval around the baseline, Visit 4, Visit 8, and change between baseline and Visit 4 as well as Visit 8 scores would be approximately 1.02 standard deviations; a paired t-test will be used to assess the change in the scores. As this is a pilot study, no adjustment in the p-value will be done for multiple comparisons.

9.3.6 To increase distress tolerance, the Impact of Event Scale (IES) will be used to assess this measure. With an n of 15, the width of the confidence interval around the baseline, Visit 4, Visit 8, and change between baseline and Visit 4 as well as Visit scores would be approximately 1.02 standard deviations; a paired t-test will be used to assess the change in the scores. As this is a pilot study, no adjustment in the p-value will be done for multiple comparisons.

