5.3 Exploratory Analyses

- 5.1.3 To assess the feasibility of conducting a telehealth support group for cancer survivors within a pandemic.
- 5.1.4 To assess YA cancer survivors' interest in participation in a telehealth support group within a pandemic.
- 5.1.5 To enhance participants' strategies for engaging social connectivity and reduce feelings of isolation amidst simultaneous forces promoting self-isolation (i.e., cancer diagnosis and pandemic).
- 5.1.6 To reduce feelings of helplessness.
- 5.1.7 To observe improvement in psychological resilience and flexibility skills in participants.
- 5.1.8 To increase distress tolerance.

Cancer within a Pandemic: A Telemental Health Intervention Designed to Augment Psychological Resilience amidst Dual Health Threats

Wake Forest Baptist Comprehensive Cancer Center
WFBCCC #01520

Table 1: Study Measures		
Type/Purpose of Measure	Variable	Measures
Primary Outcomes	Self-Efficacy	Cancer Behaviour Inventory-brief version (CBI-B)
Secondary Outcomes	Depression and Anxiety Level	CAS, MINI MAC, and Purpose in Life Test
Exploratory Analyses	Feasibility Interest Social Connectivity Psychological resilience and flexibility skills Helplessness and Hopelessness Distress tolerance	Number of subjects participating at the final visit Number of Sessions Attended UCLA Loneliness Scale Acceptance and Action questionnaire (AAQ) MINI MAC Impact of Event Scale (IES)

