9.4 Power and Sample Size

With the planned sample size is 15, a two-sided 95% confidence interval for a single proportion will extend 25.3% from the observed proportion for an expected proportion of 50%; if the proportion is low or high, such as 10% or 90%, a two-sided 95% confidence interval will extend 15.2% from the observed proportion. If the outcome is continuous, with an n of 15, power of 80% and a 2-sided alpha of 0.05, the confidence interval around the estimate would have a width of approximately 1.02 standard deviations.

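### The 15.2-point symmetric 95% interval stated for retention near 10% or 90% with 15 subjects implies impossible limits, and no interval method is named

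*Combined protocol and SAP*

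**What the plan says.** Feasibility is an exploratory objective. Its only measure in Table 1 (section 5.3) is "Number of subjects participating at the final visit". Section 9.3.1 turns this into a retention proportion: "the proportion of subjects who are active at this visit can be calculated as n/enrollment", "with the expectation of approximately 15 enrolled".

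Precision is stated in two places. Section 9.4 says: "With the planned sample size is 15, a two-sided 95% confidence interval for a single proportion will extend 25.3% from the observed proportion" when the expected proportion is 50%. For extreme values, section 9.3.1 says: "if the proportion is low or high, such as 10% or 90%, a two-sided 95% confidence interval will extend 15.2% from the observed proportion". Each section carries both figures. Section 9.3.1 adds that the data could feed sample size calculations for later studies.

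Neither section, nor any other part of the supplied document, names an interval method for a proportion or mentions cutting the limits off at 0% or 100%.

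**The concern.** A single distance from the observed proportion describes a symmetric interval. With 15 subjects and a proportion near 0 or 1, an interval that stays within 0% to 100% and keeps reasonable coverage has to be asymmetric. The plan's own example values fall where the symmetric form fails.

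Two things are at stake. First, the stated precision misleads at high retention: the shortfall that a later trial must plan for is larger than the plan says. Second, 9.3.1 defines only the point estimate, so the planning figure is the only indication of how a retention interval would be calculated. If that formula is carried into the analysis, the report could show an upper limit above 100%, or claim no uncertainty at all from 15 people.

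**Working it through.** **Inputs.** n = 15 (9.3.1 and 9.4); two-sided 95%, so z = 1.96; illustrative proportions 10%, 50% and 90% (9.3.1 and 9.4). Exactly 15 enrolled is assumed; the plan says approximately 15.

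**1. Reproduce the plan's figures.** Wald half-width = z × √(p(1−p)/n).

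- p = 0.5: 1.96 × √(0.25/15) = 0.2530, the stated 25.3 points.
- p = 0.1 or 0.9: 1.96 × √(0.09/15) = 0.1518, the stated 15.2 points.

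Other candidates at 10% or 90% do not give 15.2: the continuity-corrected Wald half-width is 18.5 points, a t quantile with 14 degrees of freedom gives 16.6, and the Wilson half-width is 15.8 and is not centred on the observed value. Wald is therefore a firm inference, though the plan does not state it.

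**2. Limits implied by the text.**

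- 90%: 90 − 15.2 = 74.8% and 90 + 15.2 = 105.2%.
- 10%: 10 − 15.2 = −5.2% and 10 + 15.2 = 25.2%.
- 50%: 50 ± 25.3 gives 24.7% to 75.3%, which is possible.

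**3. Wilson limits at the same values.** Limits = [p + z²/(2n) ± z√(p(1−p)/n + z²/(4n²))] / (1 + z²/n).

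- p = 0.9: centre (0.9 + 0.1280)/1.2561 = 0.8184, half-width 0.1581, so 66.0% to 97.7%. That is 24.0 points below 90% and 7.7 above.
- p = 0.5: 27.4% to 72.6%, or 22.6 points each way. Near 50% the stated 25.3 is not optimistic.

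Clopper-Pearson evaluated at 90% (a non-integer 13.5 of 15) gives 63.7% to 99.3%.

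**4. Attainable counts.** With 15 subjects, 10% and 90% cannot be observed (1.5 and 13.5 subjects). The 95% limits at counts that can occur are:

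| Retained | Wald | Wilson | Clopper-Pearson |
|---|---|---|---|
| 8/15 | 28.1% to 78.6% | 30.1% to 75.2% | 26.6% to 78.7% |
| 12/15 | 59.8% to 100.2% | 54.8% to 93.0% | 51.9% to 95.7% |
| 13/15 | 69.5% to 103.9% | 62.1% to 96.3% | 59.5% to 98.3% |
| 14/15 | 80.7% to 106.0% | 70.2% to 98.8% | 68.1% to 99.8% |
| 15/15 | 100% to 100% | 79.6% to 100% | 78.2% to 100% |

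The Wald lower limit exceeds the Wilson one by 4.9, 7.3, 10.5 and 20.4 points at 12, 13, 14 and 15 of 15. At 8 of 15 it is 2.0 points lower.

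**5. Coverage if the analysis used each method.** Exact coverage, summing Binomial(15, p) over all 16 outcomes:

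| True retention | Wald | Wilson | Clopper-Pearson |
|---|---|---|---|
| 50% | 88.2% | 96.5% | 96.5% |
| 60% | 93.9% | 93.9% | 98.6% |
| 70% | 95.0% | 91.5% | 98.0% |
| 80% | 81.5% | 98.2% | 98.2% |
| 90% | 79.2% | 94.4% | 98.7% |
| 95% | 53.6% | 96.4% | 99.5% |

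At a true 90%, the chance of 12, 13 or 14 retained (Wald upper limit above 100%) is 73.9%. The chance of 15 retained (zero width) is 0.9¹⁵ = 20.6%. Together that is 94.4%, from unrounded values. Of the 20.8% non-coverage there, 20.6 points are lower limits above the truth.

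**The case against.** The strongest reply is that nothing is miscalculated and that these are planning statements, not analysis rules. Both printed figures reproduce. The plan never prints 105.2% or −5.2%; those limits come from applying the stated distance. An analyst could report Wilson or exact limits without contradicting 9.3.1, so the coverage results are conditional on the planning formula being reused. This stands, and the conclusion is worded accordingly.

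The total width is also nearly right: at 90% the Wilson half-width is 15.8 points against 15.2. But the plan states a distance from the observed proportion, and that distance is wrong on both sides, too short below and too long above. Truncating at 100% would remove the impossible limit but leave the lower one at 74.8% instead of 66.0%.

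Wald is not uniformly worse. At a true 60% to 70% its coverage is equal to or better than Wilson's, and the plan gives no expected retention beyond its illustrative values. The 95% row above is not a scenario from the plan. Wilson is thus a reasonable preference, not the only acceptable method.

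Finally, the outcome is exploratory with no go/no-go threshold, and anyone with the count and denominator can recompute an interval. That limits the weight of the point but does not make the printed precision correct.

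**Conclusion.** The concern holds. The symmetric 15.2-point distance in 9.3.1 and 9.4 cannot describe a 95% interval for a proportion at 10% or 90% with 15 subjects. At 90% it understates the downside by about 9 points against Wilson (24.0 − 15.2 = 8.8) and about 11 against Clopper-Pearson (26.3 − 15.2 = 11.1). The fault is the choice of formula, not its evaluation.

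This rests on n = 15 exactly and, for the coverage and zero-width results only, on the analysis following the planning formula. The effect is confined to the stated precision and reported interval of the sole feasibility measure. The retention point estimate, the primary paired t-test and the sample size do not change. It should be corrected because the figure appears twice and the estimate is offered for planning later studies.

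**What to change.** In 9.3.1, state that the retention proportion will be reported with a two-sided 95% Wilson score interval, using the number enrolled as denominator.

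In 9.3.1 and 9.4, remove the plus-or-minus figures and give asymmetric limits at attainable counts. For Wilson with n = 15: 8/15, 30.1% to 75.2%; 12/15, 54.8% to 93.0%; 13/15, 62.1% to 96.3%; 14/15, 70.2% to 98.8%; 15/15, 79.6% to 100%. If coverage of at least 95% is wanted, name Clopper-Pearson and use its limits from the table above.

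The cost is wording in two sections and one software option. Compared with Wald, Wilson lower limits are less favourable at 10 or more of 15 and slightly more favourable at 8 or 9. Neither replacement is exact at this size: Wilson falls to 91.5% coverage at a true 70%, and Clopper-Pearson is conservative (98.0% there, 98.7% at 90%) and wider.

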This supports that focusing on a YA group for an initial study of the feasibility of an online group therapy for cancer patients is reasonable. Additionally, having a group with a higher baseline knowledge of technology as well as higher rates of skepticism of online platforms may lead to helpful feedback for future iterations of the group that will target additional patient populations. The SARS-II COVID-19 pandemic has served as a catalyst for requisite social distancing as well as increased familiarity with virtual meetings for those with the technological capacity.

Such a shared technological shift might make this type of group offering more feasible and attractive to prospective participants within the present circumstances. In response to the psychological vexations posed by simultaneous cancer and pandemic survivorship, we propose to create a virtual pandemic support group for cancer survivors that targets the constructs of health anxiety, depression, trauma, and social connectivity. The use of Acceptance and Commitment Therapy (ACT) (Arch & Mitchell, 2016) and Logotherapy (Mohabbat-Bahar et al., 2014) with cancer survivorship groups has demonstrated promising results, including the reduction of anxiety, depression, fatigue, fear of cancer recurrence, physical pain, and trauma-related symptoms, while also increasing meaning and purpose in life and a feeling of regaining some control over one's life. In line with the guiding principles of ACT and Logotherapy, this group will focus on coping strategies that enable positive psychosocial outcomes: Acceptance of cancer-related distress, reduction of cancer-related avoidance, identification of personal values, a commitment to making meaningful changes in one's behavior, and identifying meaning and purpose in life (Arch & Mitchell, 2016; Mohabbat-Bahar et al., 2014).

This will be a closed Young Adult (YA) group for the purposes of strategically covering essential skills needed for psychological flexibility, resilience, and meaning-making within these concurrent challenges to health. Pre-

Cancer within a Pandemic: A Telemental Health Intervention Designed to Augment Psychological Resilience amidst Dual Health Threats

Wake Forest Baptist Comprehensive Cancer Center
WFBCCC #01520

and post-intervention assessments will assess change over time across a variety of variables, and researchers will analyze trends in self-selection and attrition to inform future interventions.

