2.1 Primary Objective(s)

2.1.1 To improve self-efficacy for young adult cancer survivors navigating pandemic conditions

2.2 Secondary Objective(s)

2.2.1 To reduce depression and anxiety levels through meaning-making.

2.3 Exploratory Analyses:

2.3.1 To assess the feasibility of conducting a telehealth support group for cancer survivors within a pandemic.
2.3.2 To assess YA cancer survivors' interest in participation in a telehealth support group within a pandemic.
2.3.3 To enhance participants' strategies for engaging social connectivity and reduce feelings of loneliness amidst simultaneous forces promoting self-isolation (i.e., cancer diagnosis and pandemic).

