2.3.4 To observe improvement in psychological resilience and flexibility skills in participants
2.3.5 To reduce feelings of helplessness.
2.3.6 To increase distress tolerance.

Cancer within a Pandemic: A Telemental Health Intervention Designed to Augment Psychological Resilience amidst Dual Health Threats

Wake Forest Baptist Comprehensive Cancer Center
WFBCCC #01520

3 Patient Selection

Recruitment:

Investigators will attempt to recruit prospective participants through:

- Informing oncologists, APPs, and other clinicians who work with potentially eligible patients
- Advertising through hospital channels (clinic flyers, waiting room TVs, intranet postings)
- Contacting YAs who have participated in former clinical or research offerings and shared their contact information (existing databases from Psychosocial Oncology and Public Health Sciences)
- Existing psychosocial oncology caseload

Experienced Investigators within the Psychosocial Oncology group will reach out to identified patients telephonically for introduction and pre-screens. The study will be explained and patients will be asked to answer the questions on the Pre-Screening form. Individuals who are interested in participating but do not meet eligibility criteria will be referred to an alternate, general support group and informed about future offerings for which they might be eligible.

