6.0 Intervention Plan

The study aims to initially recruit a single cohort of 15 patients. This is a virtual group interventional design in which investigators distribute the electronic assessment battery, perform the intervention, assess mid-way through, and reassess post-intervention. The virtual group will be conducted within a secure platform such as Microsoft WebEx. Assessments (pre-, post-, mid-way) will be distributed through REDCap, a secure virtual platform, as will session handouts and forms. If participants do not have headphones, these will be provided by the study team. The biostatistician will assist with the assessment of change over time within the instrumentation. The session content for this group is built on clinical experience and empirically informed practices, drawing upon elements of Acceptance and Commitment Therapy and Meaning Making approaches. Investigators/facilitators believe that in these unique times, it is optimal to pull elements from various (manualized) approaches that contribute important elements to the group experience. In short, we are making intentional decisions within session design in which we draw heavily from empirically supported practices yet combine them in a manner that seems appropriate for the circumstances based on clinical judgment.

The intervention will be conducted by graduate-prepared mental health providers who are licensed or working under the supervision of a licensed provider. Providers will co-facilitate at all times, with two providers available to respond to group dynamics and follow up with individual members as needed.

The clinicians leading the group will adhere to professional, legal, and ethical guidelines of confidentiality established by professional organizations and state law. Legal and ethical exceptions to confidentiality include: A clear or present danger that the patient intends to harm her/himself or another, knowledge of the abuse or neglect of a minor child or incapacitated adult, or responses to a court subpoena or as otherwise required by law. All members of the group will be required to sign confidentiality forms, in which they agree not to disclose

Cancer within a Pandemic: A Telemental Health Intervention Designed to Augment Psychological Resilience amidst Dual Health Threats

Wake Forest Baptist Comprehensive Cancer Center
WFBCCC #01520

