6.1 Methods

Steps: (Conducted by the Psychosocial Oncology group)

1. Advertise and Identify Prospective Candidates
2. Screen all referred candidates on rolling basis
3. Send out pre-group assessments electronically for completion
4. Begin eight weeks of group work
5. Send out post-group assessments electronically for completion

Session Content

Adapted from Eilenberg, Frostholm, & Kronstrand 2014 with elements on meaning making from Breitbart & Poppito, 2005, rev. 2011:

Session 1: Introduction to ACT and Meaning Making

Summary: The purpose of the 1st session is to introduce the framework and form of the group, as well as expectations for the 8 sessions. Our main focus is on willingness to engage in treatment, a basic understanding of ACT, mindfulness, and the importance and sources of meaning making—creative, experiential, historical, and attitudinal. We will start to practice experiencing each from this first session. The purpose is to introduce the framework of the group, logistics, and to create a safe and accepting atmosphere. Furthermore, we will briefly introduce participants to an understanding of what health anxiety in the context of cancer is.

Session 2: Previous strategies for Anxiety Control

Summary: The purpose of this session is to examine the individual's control strategies and experiences in coping with health anxiety. We will introduce the concept of pain vs. suffering and how cancer can enhance life meaning, maintain life meaning, or create loss of meaning. The purpose is to help the individual to examine whether the previously used strategies have been effective in the short- and long-term in relation to living a values-based, meaningful life.

Session 3:Introduction to Values Based Living

Summary: The purpose of session 3 is to extend the insights and experiences from the last session in relation to the control agenda's limited effect on anxiety. Through experiential exercises, the effect of the control agenda is further tested and examined. Further, values-based living is introduced as an alternative to an avoidance and control-driven life. Values are introduced in the context of willingness and a discussion will introduce "Life as Legacy" both in the past, the here-and-now, and the future.

Session 4: Acceptance as an Alternative to Control

Cancer within a Pandemic: A Telemental Health Intervention Designed to Augment Psychological Resilience amidst Dual Health Threats

Wake Forest Baptist Comprehensive Cancer Center

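### Objective 2.3.2 asks about interest in joining, but Table 1 and Section 9.3.2 measure only attendance among people who already joined

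*Combined protocol and SAP*

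**What the plan says.** Objective 2.3.2 reads "To assess YA cancer survivors' interest in participation in a telehealth support group within a pandemic", and item 5.1.4 in Section 5.3 repeats it. Neither limits the question to enrolled patients.

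The exploratory row of Table 1 lists Feasibility and then Interest as its first two variables. Its first two measures are "Number of subjects participating at the final visit Number of Sessions Attended". The row alignment is lost in the text available, but Section 9.3.2 confirms the pairing: it restates the interest objective and then plans that "the data would be used to estimate the percentage of sessions attended for each participant and calculate the mean participation rate and standard deviation". It allows the same data to be given as a mean number of visits with its SD. It also says the data could help in designing later studies.

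Other sections bear on the point:
- Section 1.0 says that "researchers will analyze trends in self-selection and attrition to inform future interventions".
- Section 3 (Recruitment) lists four routes: clinicians, hospital advertising, databases of former participants, and the existing caseload. Investigators "will reach out to identified patients telephonically for introduction and pre-screens". It adds that "Individuals who are interested in participating but do not meet eligibility criteria will be referred to an alternate, general support group".
- Section 6.1, step 2, is "Screen all referred candidates on rolling basis". Section 8.0 stores the pre-screening questionnaire in REDCap.
- Section 9.3.1 measures feasibility as the proportion of enrolled subjects still active at Visit 8.

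**The concern.** Interest in joining is a property of the people who were offered the group. Sessions attended is a property of those who accepted. A plan followed to the letter would report adherence under the name of interest.

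What is at stake is the use that 9.3.2 itself names. Planning a later group takes three quantities: how many of those reached want it, how many of those eligible enrol, and how well those enrolled attend. Section 9 supplies the third, together with retention. The first two have no planned measure. No section describes a count of people contacted or of people who decline, and such counts are hard to rebuild once recruitment is over.

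**Working it through.** **Who can contribute to each measure**

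| Item | Asks about or uses | Population |
|---|---|---|
| 2.3.2 and 5.1.4 | Interest in taking part | Young adult survivors |
| Table 1, Interest | Sessions attended | Enrolled only |
| 9.3.2 | Percentage or mean number of sessions, SD | Enrolled only |
| 9.3.1 | Active at Visit 8 / enrolled | Enrolled only |
| 1.0, self-selection | No measure named | Would need joiners and non-joiners |

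The attrition half of the Section 1.0 clause has a counterpart in 9.3.1. The self-selection half has none in Sections 2, 5 or 9. By their descriptions in Section 6.2, the pre-screening questionnaire covers suitability and eligibility, and the Group Evaluation Questionnaire covers satisfaction. The latter is given only at mid-point and post-study. Neither is tied to an analysis of interest.

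**The plan's own figures.** Section 9.3.2 states none. The neighbouring half-widths in 9.3.1 reproduce with 1.96 × √(p(1−p)/n) and n = 15:
- p = 0.5: 1.96 × √(0.25/15) = 0.253, stated as 25.3%.
- p = 0.1 or 0.9: 1.96 × √(0.09/15) = 0.152, stated as 15.2%.

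These are correct, and the point does not depend on them.

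**Illustration.** From the documents: 15 participants and 8 sessions. Every other count is assumed. The interval is Wilson 95%:

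centre = (p + z²/2n) / (1 + z²/n); half-width = z√(p(1−p)/n + z²/4n²) / (1 + z²/n); z = 1.96.

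Interest, with 30 people assumed interested. For 30/60 the centre is 0.500 and the half-width is 1.96 × √(0.004167 + 0.000267) / 1.0640 = 0.123.

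| Reached (assumed) | Interest | Wilson 95% CI | 9.3.2 result if mean attendance is 6/8 |
|---|---|---|---|
| 40 | 75% | 60% to 86% | 75% |
| 60 | 50% | 38% to 62% | 75% |
| 100 | 30% | 22% to 40% | 75% |

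Uptake, with 15 enrolled out of an assumed number M confirmed eligible:

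| M | Uptake | Wilson 95% CI |
|---|---|---|
| 20 | 75% | 53% to 89% |
| 30 | 50% | 33% to 67% |
| 60 | 25% | 16% to 37% |
| 100 | 15% | 9% to 23% |

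Any of these is compatible with the same attendance result, because the number approached does not enter the 9.3.2 calculation.

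**Why interest should be split by type of contact.** People who answer an advertisement are interested before anyone calls them. Assume 60 people reached, with 95% interest among advertisement responders and 30% among the rest:
- 10 responders: (10 × 0.95 + 50 × 0.30)/60 = 24.5/60 = 41%.
- 30 responders: (30 × 0.95 + 30 × 0.30)/60 = 37.5/60 = 63%.
- 50 responders: (50 × 0.95 + 10 × 0.30)/60 = 50.5/60 = 84%.

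A pooled proportion would therefore move with the mix of routes even if interest within each route stayed the same.

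**The case against.** The best defence is that the plan is consistent with itself. Table 1 and 9.3.2 both define interest as attendance and give it a clear summary. The aim is exploratory, the study is a small pilot ("The study aims to initially recruit a single cohort of 15 patients"), and no test or decision rests on the result. Rewording the objective would remove the mismatch. All of that stands, and it limits the point to a minor one. It does not make attendance a measure of interest in joining.

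A reader might infer more than the documents support:
- *That nothing is known about people who do not enrol.* Referred candidates are screened and their questionnaires are stored. The form is not in the text, so whether it records a refusal cannot be judged.
- *That the stored questionnaires already give the number eligible.* Section 3.2 also rests exclusions on chart review, and Appendix A lists the pre-screen as one line among several.
- *That recruitment is not considered at all.* Section 9.5 sets a goal of 3 to 4 patients a week for about 4 weeks. It is a planning benchmark with no denominator, so it does not measure interest.
- *That enrolment stops at exactly 15 and later callers would be miscounted as refusals.* The documents speak of initially recruiting 15 and of approximately 15 enrolled. They state no hard cap.
- *That the self-selection clause is a broken commitment to a stated objective.* It is one clause in the background, and its attrition half is met.

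**Conclusion.** The mismatch holds on the text: the objective asks about interest in participating, and the planned measure is adherence among those who already joined. Section 9 as a whole describes only enrolled people. The self-selection analysis mentioned in Section 1.0 is not carried through, and no count of people contacted or declining is described.

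The severity is minor. One exploratory aim is affected, and the primary and secondary analyses do not depend on it. The percentages above show the mechanism under assumed counts and do not estimate the size of the problem, since the documents give no number contacted, interested, eligible or declining. What does not rest on those assumptions is that the attendance result carries no information about how many people were approached.

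**What to change.** 1. In Table 1 and 9.3.2, relabel sessions attended as adherence and keep its mean and SD.
2. Keep a simple recruitment tally with one entry per person, so that repeat calls and people found by two routes count once. Record recruitment route, contacted, not reached, interested, declined, ineligible and consented.
3. Report interest as interested / reached, counting interested-but-ineligible people as interested. Give it separately for staff-initiated contact and for people who responded to advertising.
4. Report uptake as consented / confirmed eligible after both pre-screen and chart review.
5. Give each as a count with a Wilson 95% interval, descriptive only, and say that it applies to those approached. A finer split by route would be too thin: 15 consents over four routes average 15/4 = 3.75 each.
6. Do not present the tally as an analysis of how joiners differ from decliners. It holds route and outcome but no personal characteristics, so it cannot show that.

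If no tally is kept, the minimum is to reword 2.3.2 and 5.1.4 as attendance among enrolled participants.

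The cost is wording plus a small staff task, best started before recruitment. For an assumed 40 to 100 people over the planned 4 weeks, that is 40/4 = 10 to 100/4 = 25 entries a week. No visits or questionnaires are added.
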